9.6 Criteria and Reasons for Terminating Trial Based on Statistical Reasons

No interim analysis will be performed for this study, therefore, no standard for terminating the trial for statistical reasons is developed.

9.7 Statistical Methods of Data, Together with Processing Methods of Missing, Unused or Wrong Data and Unreasonable Data

9.7.1 Statistical method for data

Statistical analysis is performed using the SAS 9.1 software.

Statistical description on all data, including demographic data, baseline data, all efficacy indicators and all safety data shall be performed. Measurement data will be statistically described using mean, standard deviation, minimum, maximum, median, 25th percentile and 75th percentile; enumeration data will be statistically described using frequency and percentage.

The primary effectiveness evaluation indicator (anastomosis success rate) is evaluated by the confidence interval method.

The secondary evaluation indicators are evaluated by the difference test. Measurement data are compared using two independent samples t-test or Wilcoxon rank sum test. Enumeration data are compared using Pearson's X^2 test or Fisher's exact test.

The safety evaluation indicators are evaluated by the difference test. Enumeration data are compared using Pearson's X^2 test or Fisher's exact test. The adverse events and device defects occur in this trial shall be shown in list.

The stapler operational performance is evaluated by the difference test. Enumeration data are compared using Pearson's X^2 test or Fisher's exact test.

The central effect is considered in the analysis process. The general linear model is used for measurement data, and CMH or logistic regression is used for enumeration data.

9.7.2 Missing, unused, or incorrect data (including dropouts and withdrawals) and unreasonable data

All missing, unused or incorrect data (including dropouts and withdrawals) and unreasonable data will be discussed and finally determined by the investigators and biostatistician in the data review stage. The basic statistical principles for the processing of these data are as follows:

- (1) The details of each drop-out case shall be described, and the drop-out between the test group and the control group shall be compared using Pearson X^2 test or Fisher exact test;
- (2) Missing data at baseline shall not be estimated;
- (3) Missing values of main evaluation indicator (success rate of anastomosis) shall not be estimated;

Clinical Trial on Performance and Safety of Disposable Powered Articulating Endoscopic Linear Cutter Stapler in Gastrointestinal Tissue Cutting and Anastomosis

- (4) Missing values of secondary evaluation indicators shall not be estimated;
- (5) Missing values for operational performance evaluation shall not estimated;
- (6) The wrong and unreasonable data shall be regarded as missing values;
- (7) Missing values for all safety measures shall be estimated using the worst case;
- (8) Sensitivity analysis shall be performed on the safety data set for all the safety evaluation indicators after treatment.
- (9) Missing data shall be statistically analyzed in the table.

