8.1.3 Selection of test method and reasons

This clinical trial is a "prospective, multi-center, stratified-block randomization, incomplete blinding, parallel

positive control, non-inferiority test".

- (1) Prospective: A research method that tracks from the present to the future. Prospective studies can clarify the causal relationship; uniform diagnostic, detection, and evaluation criteria can be available for the obtained data, the data processing therefore is controllable.
- (2) Multi-center: 5 clinical trial institutions were selected to conduct this clinical trial. The application of multi-center trial can allow to obtain more cases than those of single-center trial in the same time, the clinical trial time therefore can be shortened; since the multi-center trial is completed by different regions, different trial centers and many clinical researchers, the conclusion therefore is often widely representative.
- (3) Stratified block randomization: This trial adopts the stratified block randomization method (with the study site as the stratification factor) and the randomization envelope to randomize the subjects who are screened successfully. The randomized-grouping time is when the subjects sign the ICF, which also meets the inclusion and exclusion criteria in the protocol at the same time. Randomized grouping ensures that, except for treatment factors, other non-treatment factors that may have confounding effect are kept consistent in each group as far as possible, so as to ensure the balance of baseline of each group; randomized-grouping allows each subject to have equal opportunity to be assigned to the test group or control group.
- (4) Incomplete blinding: Since the investigational medical device and the control medical device are different in appearance, while the subjects are under anesthesia during the operation, the grouping arrangement can not be known. Therefore, the method of incomplete blinding is used, that is, the investigators knows the grouping result, while the subject does not know the grouping result. The blinding method can minimize the bias caused by "placebo effect" and investigator bias; for the less precise observation indicators, it can significantly reduce the bias; and make the evaluation of adverse reactions by investigators and subjects more objective.

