8.2.4 Blinding method

The investigators could not be blinded due to the difference in appearance between the test device and the control device, this trial therefore adopted an incomplete blinding method, and the subjects were not informed of the randomization results (i.e., the subjects did not know their own treatment assignment).

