9.9 Selection Criteria and Reasons for Subjects Included in Analysis

- (1) Full analysis set (FAS): According to the basic principles of intention to treat analysis, all the subjects who have received at least one treatment with the investigational medical device and had at least one post-baseline observation data are included in the FAS. The FAS will be used as the primary population for baseline data (and efficacy evaluation) in this study.
- (2) Per-protocol set (PPS): It refers to the subjects in the FAS who do not seriously deviate from the trial protocol, have good compliance and have no missing primary efficacy indicators. The PPS will be used as the primary population for efficacy analysis in this study.
- (3) Safety set (SS): All subjects who have received at least one treatment with the investigational medical device and had at least one safety evaluation. The SS will be used as the primary population for safety analysis in this study.

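### Section 9.7.2 lets investigators who know the allocation help decide whether a primary outcome becomes missing, and a voided primary outcome removes the subject from the per-protocol set

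*Combined protocol and SAP*

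**What the plan says.** Section 9.7.2 deals with missing, incorrect and unreasonable data. Such data "will be discussed and finally determined by the investigators and biostatistician in the data review stage". Item (6) then states: "The wrong and unreasonable data shall be regarded as missing values". Neither term is defined, and the primary outcome is not exempted. Item (3) adds: "Missing values of main evaluation indicator (success rate of anastomosis) shall not be estimated".

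On masking, section 8.1.3 (4) says that "the investigators knows the grouping result", and section 8.2.4 gives the reason: "The investigators could not be blinded due to the difference in appearance between the test device and the control device". Whether the biostatistician is masked is not stated.

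On analysis sets, section 9.9 (2) admits to the PPS only those full-analysis-set (FAS) subjects who, besides having no serious deviation, "have good compliance and have no missing primary efficacy indicators". It continues: "The PPS will be used as the primary population for efficacy analysis in this study". Section 9.9 (1) also labels the FAS as primary for baseline data and efficacy evaluation. Section 9.4 lists missing primary data among the reasons for dropping out of the primary analysis and has the principal investigator confirm such cases.

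The remaining controls are these. Section 10.3 calls for a verification plan approved before the first data arrive, and for queries on doubtful data. Section 10.4 has the data review report and the division into analysis sets settled before lock. Section 9.7.2 items (7) and (8), on worst-case handling and sensitivity analysis, concern safety indicators.

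**The concern.** Under section 8.1.15.1 the outcome is judged during surgery from the integrity of the staple line, leakage and bleeding. Where there is a conversion, the investigators also judge whether the stapler caused it. The people who score the endpoint know the arm, and they later share the decision on whether a recorded value is unreasonable. If that value is the primary outcome, four rules act in sequence: it becomes missing, it is not imputed, the subject fails the PPS condition, and the PPS carries the efficacy analysis. No stated criterion limits the judgement and no masking protects it.

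The design expects very few failures. Voiding a test-arm failure lowers the numerator and denominator of the test failure rate together and moves the confidence limit towards a pass. The non-inferiority conclusion, and its error rate, would then depend in part on a decision made with knowledge of the arm.

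**Working it through.** **Inputs from the plan.** Section 9.2.1: success 97% in both arms, margin 10 percentage points, one-sided alpha 0.025, power 80%, 1:1 allocation, 65 evaluable and 82 enrolled per arm. Section 9.5: non-inferiority if the lower 95% limit of test minus control exceeds -10%.

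**The plan's own figure.**
- n = 2 × 0.97 × 0.03 × (0.8416 + 1.9600)² / 0.10² = 45.7.
- Corrected: (45.7/4) × [1 + √(1 + 4/(0.10 × 45.7))]² = 64.1, so 65.
- 65/0.80 = 81.25, so 82 per arm and 164 in total. The stated figures reproduce.
- Expected failures per arm at 97%: 82 × 0.03 = 2.46.

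**Assumptions for the illustration.** The plan names only a confidence interval method, so both Newcombe and Wald are shown. The event counts, and the choice to void test-arm failures while leaving the control arm untouched, are assumptions.

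**Formulas.** With observed rates pT and pC:
- Wald: (pT − pC) − 1.96 × √[pT(1 − pT)/nT + pC(1 − pC)/nC].
- Newcombe: (pT − pC) − √[(pT − lT)² + (uC − pC)²], where lT is the lower Wilson limit for test and uC the upper Wilson limit for control.

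Example, 76/82 v 80/82: pT = 0.9268, lT = 0.8494, pC = 0.9756, uC = 0.9933. Newcombe gives -0.0488 − √(0.0774² + 0.0177²) = -0.0488 − 0.0794 = -12.8%.

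**Lower limits against control 80/82.**

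| Test arm | Newcombe | Wald |
|---|---|---|
| 76/82 (6 failures) | -12.8%, fails | -11.4%, fails |
| 76/81 (one voided) | -11.4%, fails | -9.95%, passes |
| 76/80 (two voided) | -9.9%, passes | -8.4%, passes |
| 77/82 (5 failures) | -11.3%, fails | -9.8%, passes |
| 77/81 (one voided) | -9.8%, passes | -8.3%, passes |

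One voided outcome can reverse the conclusion under either interval. The starting count at which it does so differs: five test failures under Newcombe, six under Wald.

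**Type I error.** Exact binomial enumeration, true rates 87% (test) and 97% (control), 82 per arm:

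| Test failures voided | Newcombe | Wald |
|---|---|---|
| 0 | 2.1% | 4.3% |
| 1 | 4.7% | 8.7% |
| 2 | 8.6% | 12.5% |

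The Wald value with nothing voided already exceeds 2.5%. That comes from the interval and not from the voiding rule.

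**How often it would matter if the devices are equal.** At 97% in both arms, six or more test failures in 82 has probability 3.7%. Voiding one test failure wherever there is one turns a fail into a pass in about 8% of trials (Newcombe) or 3% (Wald). Voiding two does so in about 12% or 4%.

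**The case against.** The best defence is that the exposure is narrow and partly guarded. The endpoint is binary with written criteria, so a recorded failure is harder to call unreasonable than an out-of-range laboratory value. Doubtful data go to query under section 10.3. The biostatistician shares the decision. Each drop-out is described and drop-out is compared between arms (section 9.7.2 item 1), and missing data are tabulated (item 9). Section 9.1 leaves detail to an analysis plan finalized before lock, which may supply criteria. These points limit the exposure, but none of them masks the review or keeps the primary outcome out of item (6).

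Three stronger readings are tempting and are not supported.
- A reader might infer that any voided value removes the subject. The missing-value condition in section 9.9 (2) concerns the primary indicator only; a voided laboratory, timing, baseline or secondary value does not by itself exclude anyone.
- A reader might infer that the decision is taken once the trial's results are known. Investigators know the arm and outcome of their own subjects. However, section 10.4 settles the analysis sets before lock and passes the data to the statisticians after it, and section 9.6 rules out interim analysis. Nothing says that comparative results exist at data review.
- A reader might infer that only the PPS counts, since it is named primary. Section 9.9 (1) gives the FAS a similar label. A subject may stay in the FAS, but the unimputed outcome is still absent there, and the plan does not say whether that subject remains in the denominator.

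It is also true that the counts above are borderline cases. The conclusion changes only when the result lies near the margin.

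**Conclusion.** The point holds in this limited form. The text gives a route by which people who know the arm can help to void a primary outcome and so take the subject out of the PPS, with no masking, no stated criterion and no efficacy sensitivity analysis to show the effect. It does not show that the route was used or that anyone intends to use it.

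The size depends on how many outcomes are voided and in which arm, neither of which the documents give. Voiding one test-arm failure roughly doubles the one-sided type I error under either interval; voiding two raises it about fourfold (Newcombe) or threefold (Wald). The sample size is unaffected. This should be corrected before lock, in proportion to the low cost of doing so.

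**What to change.** In section 9.7.2:
- Hold the pre-lock data review on listings without treatment arm.
- Let investigators answer source queries under section 10.3, but not decide which values are voided or which subjects are excluded. Align the confirmation step in section 9.4 with this.
- Exempt the primary outcome from item (6), so that a source-verified success or failure is always kept.
- Add a sensitivity analysis on the FAS that counts any primary outcome that cannot be verified as a failure. Counting it as a failure in the main analysis would replace item (3) outright and is debatable, so it belongs in the sensitivity analysis.
- List every changed or voided primary value by arm in the report.

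The cost is wording, one masked listing before lock and one extra analysis. No new data collection is needed.

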9.8 Procedures for Reporting Deviations from Original Statistical Plan

In general, only the statistical analysis contents pre-specified in the statistical analysis plan can be presented in the clinical trial report of this trial. The increased need for statistical analysis due to various indeterminate reasons will be considered exploratory only.

9.9 Selection Criteria and Reasons for Subjects Included in Analysis

- (1) Full analysis set (FAS): According to the basic principles of intention to treat analysis, all the subjects who have received at least one treatment with the investigational medical device and had at least one post-baseline observation data are included in the FAS. The FAS will be used as the primary population for baseline data (and efficacy evaluation) in this study.
- (2) Per-protocol set (PPS): It refers to the subjects in the FAS who do not seriously deviate from the trial protocol, have good compliance and have no missing primary efficacy indicators. The PPS will be used as the primary population for efficacy analysis in this study.
- (3) Safety set (SS): All subjects who have received at least one treatment with the investigational medical device and had at least one safety evaluation. The SS will be used as the primary population for safety analysis in this study.

9.10 Exclusion of Special Information During Hypothesis Validation and Reasons

Not applicable.

10. Data Management

10.1 Database Design

The CRF designer is responsible to annotate the final version of the blank CRF and describe in detail the necessary elements (e.g., variable name, length, type, range of the database variable, etc.).

The database designer determines the requirements for database establishment and database structure according to CRF and annotated CRF, and designs the database.

The database must be thoroughly tested to ensure that the contents and structure of the database are consistent with those of the CRF and annotated CRF, that the specified data are appropriately entered into the

database, and that the entered data points are correctly exported into the corresponding database variables.

The database can be officially released for use only after it is approved.

10.2 Data Receipt and Data Entry

Data may be received by mail, courier with tracking for confidentiality, hand delivery by the monitor, web entry, or other electronic means. When the paper CRF data is received, it shall be recorded in the data receiving record form. After the completion of data receiving, the CRF shall be scanned and backed up; the data received via network or other electronic means shall be stored in the corresponding documents and records to confirm the data source.

Data entry can be double-entered by blind verification (two persons independently enter the data, and the inconsistency is resolved at the second entry), and double-entered by interactive verification (the second entry resolves the inconsistency between the two entries, and pays attention to the value of the first entry), manual review of single entry and other forms.

Prior to data entry, the data manager shall train the entry clerk or investigators on system operation or matters specific to this study.

After the completion of data entry, the database data shall be checked with original data to ensure that the database data are consistent with original data.

10.3 Management of Data Verification and Query

Data verification includes manual inspection of data, and computer verification designed for identification error, invalid data range, data integrity, protocol violation and consistency inspection. Data administrator shall complete relevant procedures of preparing and approving the Data Verification Plan before the first data receipt to determine the data verification content. Programmer will program and test the verification procedure according to the finalized Data Verification Plan.

Based on the results of manual inspection and computer verification, the data administrator will resolve the doubtful data in the form of data query form, data processing agreement and self-evident correction, and update the database according to the answers or descriptions in relevant documents.

10.4 Database Lock and Data Archiving

The clinical trial database must be closed and locked to ensure the consistency and integrity of the data results, data analysis and data submitted to the official authorities.

When all data have been received and all data cleaning has been completed, all queries have been answered, all unanswered questions have been explained, the data review report has been confirmed, the division of statistical analysis dataset has been clarified, and the data quality control has been completed (the database quality is up to standard), the data administrator shall apply for database locking to the project team members.

After being jointly confirmed by the investigators, the sponsor and project team members, the data editing authority of the database will be taken back to lock the database. After the database is locked, the data administrator shall transfer the data to the statistical analysis department in a timely manner. If data correction is required, the review and approval of Database Unlock Application Form shall be completed, and the database shall be unlock, so that corresponding personnel can enter the database to correct the data.

The data administrator shall establish the Data Management Project Folder, and shall be responsible for archiving the data or record files when they meet the conditions for archiving. Upon completion of the study, the data administrator will revoke the database access of relevant personnel, create a copy of the database, and archive the study documents and data management documents.

11. Feasibility Analysis

11.1 Probability Analysis of Success

- (1) According to the relevant clinical trials, it shows that such product is safe and reliable; and such product has been used in clinical practice for many years, and its safety and reliability have been verified.
- (2) The company producing the study medical device has rich experience. The product quality is reliable and meets the requirements of clinical trials; the device has passed the product registration inspection designated by NMPA (original CFDA).
- (3) The clinical institutions undertaking this trial have complete instruments, equipment and technical resources.
- (4) The investigators are excellent academic leaders in related disciplines in China, all of whom are physicians at or above the deputy director level, have rich clinical trial experience, have received GCP and relevant training, and can carry out treatment in strict accordance with the clinical trial protocol.

11.2 Probability Analysis of Failure

- (1) Too many subjects withdrawing from the trial due to SAE;
- (2) Too many subjects lost to follow-up;
- (3) The IFU and label information of test product can not effectively instruct the operator;
- (4) Unskilled operation of investigators.

11.3 Conclusion

In conclusion, this product can be used for the anastomosis of gastrointestinal tissues to benefit relevant patients. This study has great feasibility and high possibility of success.

12. Quality Control of Clinical Trial

12.1 Quality Assurance

12.1.1 Definition

Quality assurance is defined as planned and systematic activities. These activities are established to ensure that the study, generation, citation (recording) and reporting of data are conducted in compliance with *Good Clinical Practice* (GCP) and applicable regulatory requirements.

12.1.2 Audit

Audit refers to a systematic independent inspection of clinical trial-related activities and documents organized by the sponsor to determine whether the implementation of such activities and the recording, analysis and reporting of data comply with the clinical trial protocol, standard operating procedures, GCP and relevant applicable management requirements.

12.1.3 Inspection

Inspection refers to the activities of the food and drug regulatory authority in reviewing and supervising relevant documents, facilities, records and other aspects of a clinical trial.

12.1.4 Clinical trial monitoring

The sponsor shall be responsible for comprehensively tracking and monitoring the implementation of clinical trial, ensuring that the trial is conducted in compliance with GCP and relevant regulations, and is in compliance with the trial protocol. NMPA (original CFDA) may also inspect the clinical trial during or after the trial is completed, and promptly notify the sponsor if investigators receive such notification.

The monitor will make periodic visits to the conduct and completion of the trial. Monitors will check the completeness of case records, the accuracy of case report form content, verify trial data, check the investigator's compliance with the trial protocol and the GCP, and ensure the accuracy of distribution, storage and counting of the study device.

